7.1.2.5. Statistical Analyses/Methods

Hgb Efficacy Co-Primary Statistical Analyses
Endpoint(s)

 • Mean change in Hgb between baseline and EP
Model Specification

 • Hgb during the EP will be defined as the mean of all available post-randomization Hgb values (on and off-treatment) during the EP (Week 28-52). • The ANCOVA model used to quantify the difference in mean Hgb change will adjust for the following baseline values: 
 ○ Treatment ○ Baseline Hgb (see Section 10.5.2) ○ Current ESA use (as randomized, see Section 10.10.2) ○ Region (as randomized, see Section 10.9 & Section 10.10.2)
Multiple Imputation Analysis

 • Multiple imputation analysis will be performed using all available Hgb values (on and off-treatment) and conducted under a set of assumptions about missing Hgb values (see Section 10.6.3). 
 ○ Intermittent missing post-baseline scheduled Hgb data in both arms through Week 52 will be imputed using PROC MI procedure with NIMPUTE = 200 and MCMC IMPUTE = monotone to generate 200 datasets with only monotone missing patterns. Burn in iterations (NBITER) and maximum iteration (MAXITER) will both be set to 500. The seed for reproducibility is set to 200808. The imputations will be done by randomized treatment, current ESA use at randomization, and region. ○ For each of the monotone missing dataset (out of the 200 imputed as indicated above), the missing scheduled Hgb values through Week 52 will be imputed based on the MAR assumption and will be performed using PROC MI by treatment, current ESA use at randomization, and region. The monotone regression will have baseline Hgb, prior scheduled (possibly imputed) Hgb values, and may include current ESA use at randomization and region as covariates (see Model Checking & Diagnostics, below).

Hgb Efficacy Co-Primary Statistical Analyses

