
The seed for reproducibility is set to 200808.
 
 ○ The low and high cutoffs at Hgb values of 6 g/dL and 15 g/dL will be applied to all imputed Hgb values. ○ EP Hgb values will be computed and compared across treatment groups using the co-primary ANCOVA model described above. Rubin's rules [Rubin, 1987] will be used to combine results of the imputed datasets using SAS PROC MIANALYZE procedure. As a result, a single estimated treatment difference and its standard error will be produced, with which a 95% CI will be calculated.
Model Checking & Diagnostics

 ● Refer to Appendix 12: Model Checking and Diagnostics for Statistical Analyses.
Model Results Presentation

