
 ● All available observed Hgb values (on and off-treatment) will be summarized using mean, standard deviation, minimum, P25, median, P75 and maximum at each visit by treatment group. In addition to scheduled visits, the baseline value and mean MP, mean EP, mean Alt EP, and end of treatment values will be included (see Section 10.6.3). This summary is repeated by current ESA use at randomization. 
 ○ This summary of Hgb will also be repeated for visits up to and including Week 52, using the data used for the primary Hgb analysis (i.e., including imputed values (see Section 10.6.3)), and by current ESA use at randomization. ● All available observed Hgb change from baseline values (on and off-treatment) will also be summarized using mean, standard deviation, minimum, P25, median, P75, and maximum at each post-baseline visit, including the mean MP, mean EP, mean Alt EP, and end of treatment values (see Section 10.6.3). This summary is repeated by current ESA use at randomization. 
 ○ This summary of Hgb will also be repeated for visits up to and including Week 52, using the data used for the primary Hgb analysis (i.e., including imputed values (see Section 10.6.3)), and by current ESA use at randomization. ● The number and percentage of subjects with imputed data in the primary Hgb analysis will be provided by treatment group. The number and percentage of subjects by reason for data imputation will be provided. Reasons include: intermittent missing Hgb values, death before Week 28, death during Weeks 28 – 52, investigator site closed before Week 28, investigator site closed during Weeks 28-52, lost to follow-up before Week 28, lost to follow-up during Weeks 28 – 52, consent withdrawn before Week 28, consent withdrawn during Weeks 28 – 52, EOS visit occurred before Week 28, EOS visit occurred during Weeks 28-52, and other monotone missing Hgb values. Subjects will be further classified as either having observed all 7 scheduled EP Hgb values, having observed a partial schedule of EP Hgb values, having observed no scheduled EP Hgb values with at least one unscheduled EP Hgb value, or having observed no EP Hgb values, scheduled or unscheduled. For subjects with partial scheduled EP Hgb values, both the pattern of imputed data (intermittent, monotone) and the amount of imputed data (1 – 6 scheduled Hgb values missing) will be summarized. For subjects with partial scheduled EP Hgb values and a monotone imputed data pattern, the reason for the monotone imputed scheduled EP Hgb values will be provided. Reasons include: death during Weeks 28-52, investigator site closed during Weeks 28-52, lost to follow-up during Weeks 28 – 52, consent withdrawn during Weeks 28 – 52, EOS visit occurred during Weeks 28-52, and other monotone imputed Hgb values. And for summaries of the amount of missing scheduled EP Hgb values, the presence or absence of additional unscheduled EP Hgb values will be summarized.

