
Hgb Efficacy Co-Primary Statistical Analyses

- The least square (LS) mean estimates and standard errors by treatment group, LS mean difference, two-sided 95% CI and one-sided non-inferiority p-value for the difference in the co-primary Hgb endpoint between the daprodustat and darbepoetin alfa arms from the ANCOVA model will be presented. The number of subjects contributing to the analysis and the associated mean and standard deviation of the baseline and EP Hgb values will also be displayed with the results of the ANCOVA model.
- The LS mean difference and associated two-sided 95% CI will be displayed on a forest plot together with supportive analysis results (excluding the Tipping Point Analysis).
- All available observed Hgb values (on and off-treatment) will be displayed graphically for each scheduled study visit using a line plot. The line plot of mean values and 95% CIs by time will include horizontal reference lines to depict the Hgb analysis range (10-11.5 g/dL), vertical reference lines to identify the EP (weeks 28-52), and the number of subjects by treatment group contributing to each mean value. The plot will be repeated by current ESA use at randomization.
 - This figure will also be repeated for visits up to and including Week 52, using the data used for the primary Hgb analysis (i.e., including imputed values). (see Section 10.6.3)).
- All available observed Hgb change from baseline values (on and off-treatment (see Section 10.6.3)) will be displayed graphically for each scheduled study visit using a line plot. The line plot of mean values and 95% CIs by time will include vertical reference lines to identify the EP (Weeks 28-52), and the number of subjects by treatment group contributing to each mean value. The plot will be repeated by current ESA use at randomization.
 - This figure will also be repeated for visits up to and including Week 52, using the data used for the primary Hgb analysis (i.e., including imputed values). (see Section 10.6.3)).
- A listing of all hemoglobin values will be provided, including treatment, most recent dose, site ID, unique subject ID, visit, assessment date, select demographic information and central laboratory and HemoCue Hgb values.

Model Results Interpretation

- Non-inferiority will be achieved if the lower limit of the two-sided 95% CI of the treatment difference is greater than the pre-specified non-inferiority margin of -0.75 g/dL.

Sensitivity Statistical Analyses

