10.6.3. Efficacy

10.6.3.1. Hemoglobin Endpoints

Hemoglobin Values
Central Laboratory and HemoCue Hgb Values

 ● When source of Hgb measurement is not specified: 
 ○ For reporting purposes, central laboratory Hgb values will be used, unless otherwise specified. However, if a central laboratory Hgb value is missing, a corresponding non-missing HemoCue Hgb value will be used. This approach will

Hemoglobin Values

be used for the co-primary Hgb analysis.
 
 Some displays may be created for either central laboratory Hgb values only or HemoCue Hgb values only. The central laboratory summary will be considered the primary summary in this case.
Evaluable Hemoglobin Values

 Evaluable Hgb values are on-treatment Hgb values (see Section 10.4.1) that are not taken within the 8 weeks following a red blood cell transfusion, a whole blood transfusion, or a non-randomized ESA treatment which occurs on or after the randomization date. Red blood cell transfusions, whole blood transfusions and non-randomized ESA treatments occurring on or after the randomization date are identified by comparing the start and stop date of the respective transfusion or ESA concomitant medication record to the randomization date.
Imputed Hemoglobin Values

 For each missing value between baseline to Week 52 (inclusive), 200 imputed values will be generated using the multiple imputation method (see Section 7.1.2). The average of these 200 imputed values will be used as the value for this missing value in the summary tables and figures. For co-primary efficacy Hgb analysis and the corresponding subgroup analyses using all available observed and imputed Hgb values (on and off-treatment), Rubin's rules [Rubin, 1987] will be used to combine results of the imputed datasets using SAS PROC MIANALYZE procedure.
EP Hemoglobin Value for Co-primary Hgb Analysis

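### The repeated Hgb displays that include imputed values use the average of 200 imputations, so their SDs, quantiles and 95% CIs are too tight (minor)

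*SAP*

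**What the plan says.** Section 7.1.2.5 describes a multiple imputation run "to generate 200 datasets with only monotone missing patterns", after which the remaining gaps are filled under missing at random. For the co-primary ANCOVA, Rubin's rules "will be used to combine results of the imputed datasets using SAS PROC MIANALYZE procedure".

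The displays follow a different rule. Section 10.6.3.1 (Imputed Hemoglobin Values) states: "The average of these 200 imputed values will be used as the value for this missing value in the summary tables and figures". Its next bullet prescribes Rubin's rules for the co-primary analysis and its subgroup analyses, but not for displays.

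Under Model Results Presentation in Section 7.1.2.5, the lead table uses observed values, which "will be summarized using mean, standard deviation, minimum, P25, median, P75 and maximum at each visit by treatment group". A sub-bullet then adds: "This summary of Hgb will also be repeated for visits up to and including Week 52, using the data used for the primary Hgb analysis". Change from baseline is handled in the same way. For the figures, the lead plot is again of observed values, and its format is set there: "The line plot of mean values and 95% CIs by time will include horizontal reference lines to depict the Hgb analysis range". Its sub-bullet adds: "This figure will also be repeated for visits up to and including Week 52, using the data used for the primary Hgb analysis". The sub-bullets refer back to Section 10.6.3, and so to the averaging rule.

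**The concern.** Multiple imputation draws each missing value with random error so that the completed data have the right spread, and so that disagreement between datasets measures what is unknown. Averaging the 200 draws for a subject and visit undoes both. What is left is close to the conditional mean given the subject's other data, and it is then counted like a measured value.

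The repeated tables report SD, minimum, quartiles and maximum, and the repeated plots report 95% CIs. These are the quantities that averaging distorts. The text also presents the displays as showing the data of the primary analysis, which never uses an averaged dataset. A reader comparing visits or arms could take a narrower band as lower Hgb variability or better precision when it only reflects more missing data.

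**Working it through.** **No figure to reproduce.** The SAP states no SD, CI width or missing fraction for these displays, so the size has to be shown over assumed ranges.

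**Inputs**
- Number of imputations: 200 (Section 7.1.2.5).
- Limits on imputed values: 6 and 15 g/dL (Section 7.1.2.5).
- Subjects per arm: 4,500 randomized 1:1 (Section 2.3), so 4,500 / 2 = 2,250.
- Assumed: fraction missing at a visit *f* = 5–30%; variance explained by the imputation model R² = 0.2–0.6; Hgb SD 1.0 g/dL; values missing completely at random in the check.

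**Formulas**, with σ the true SD and *n* the arm size:
- SD from averaged values ≈ σ √(1 − f(1 − R²)).
- SE from averaged values ≈ σ √[(1 − f(1 − R²)) / n].
- SE by Rubin's rules ≈ σ √[(1 − fR²) / ((1 − f) n)].
- CI-width ratio, averaged to Rubin = √[(1 − f(1 − R²))(1 − f) / (1 − fR²)].

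Visit means do not move. Averaging is linear, so the mean of the averaged fill-ins equals the average of the 200 dataset means.

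**Results** (ratios to the correct value)

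| f | SD ratio, R² 0.2 / 0.4 / 0.6 | CI-width ratio, R² 0.2 / 0.4 / 0.6 |
|---|---|---|
| 5% | 0.980 / 0.985 / 0.990 | 0.960 / 0.970 / 0.980 |
| 10% | 0.959 / 0.970 / 0.980 | 0.919 / 0.939 / 0.959 |
| 20% | 0.917 / 0.938 / 0.959 | 0.837 / 0.875 / 0.915 |
| 30% | 0.872 / 0.906 / 0.938 | 0.752 / 0.808 / 0.867 |

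SDs are therefore about 1–13% too small and CIs about 2–25% too narrow.

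**Absolute size at f = 20%, R² = 0.4, SD 1.0, n = 2,250**
- Averaged: SE = √(0.88 / 2,250) = 0.0198; half-width 1.96 × 0.0198 = 0.0388 g/dL.
- Rubin: SE = √[0.92 / (0.8 × 2,250)] = 0.0226; half-width 1.96 × 0.0226 = 0.0443 g/dL.
- Difference: 0.0443 − 0.0388 = 0.0055 g/dL, or 0.0055 / 0.75 ≈ 0.7% of the non-inferiority margin.
- Implied coverage of a nominal 95% interval: 2Φ(1.96 × 0.875) − 1 ≈ 91%.

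**Simulation check.** One arm of 2,250 was simulated with proper regression imputation, 200 imputations, the 6 and 15 g/dL limits and 60 replicates per scenario. At f = 20% and R² = 0.4, the SD was 0.937 from averaged values against 0.999 from the imputed datasets. The SEs were 0.0198 and 0.0226, a ratio of 0.875. Means agreed to rounding error. Sixty replicates are too few to estimate coverage, so the coverage above comes from the formula.

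**The case against.** The mechanism is hard to dispute, but there is a good case that it matters little, and most of that case stands.

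- **A reader might infer that these are the principal Hgb profiles.** They are not. In Section 7.1.2.5 the lead tables and plots use observed values only, and the 95% CI format is set in that observed-values bullet. The averaged values enter only through the sub-bullets that repeat the displays to Week 52. Readers will have the unaffected versions alongside.
- **A reader might infer that the non-inferiority result is falsely precise.** It is not. The co-primary ANCOVA, the tipping-point analysis and the subgroup analyses on imputed data all use Rubin's rules. The forest plot shows model-based differences.
- **A reader might infer that the narrowing is worst at the last visits, or in one arm.** The SAP does not support either. After permanent discontinuation, Section 10.2.1.3 schedules first-year visits at Weeks 4, 16, 28, 40 and 52. Four of the seven evaluation-period visits (Weeks 32, 36, 44 and 48) are therefore unscheduled for those subjects, and missingness may peak there rather than at Week 52. No imbalance between arms is shown.
- **Part of the handling is disclosed.** The sub-bullets point to Section 10.6.3, and a by-arm table of imputed data with reasons and patterns is planned. That tells the reader how much was imputed; it does not correct the SDs or error bars.
- **R² may be higher for intermittent gaps,** because the MCMC step can use later as well as earlier visits. That would put those values towards the lower end of the range.

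The SAP also does not say how the plotted CI is computed. Even so, a dataset with one averaged value per gap holds no between-imputation variance, and no correction is given.

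**Conclusion.** The point holds as a minor one. Followed as written, the rule gives SDs, quartiles, extremes and 95% CIs that are too tight in the repeated Hgb and change-from-baseline displays, and those displays do not show the data that the primary analysis uses. The direction follows from the averaging itself. The size (SDs about 1–13% too small, CIs about 2–25% too narrow) rests on the assumed 5–30% missing and R² of 0.2–0.6. The absolute effect on a CI half-width is around 0.005 g/dL in the mid-range case with 2,250 per arm. It is largest at whichever visits have the most missing data. No estimate, test or decision in the trial depends on it.

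**What to change.** In Section 10.6.3.1, replace the averaging rule for displays. For tables and figures that include imputed values, compute each statistic within each of the 200 datasets. Pool the means and their CIs by Rubin's rules, and average the SDs and quantiles over imputations. Apply this to Hgb and to change from baseline, and state in Section 7.1.2.5 how the plotted CI is obtained.

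In the simulation this restored the SD (0.997–1.003 pooled, against 0.997–1.002 in the full data) and left the means unchanged. Over the assumed range the CIs become about 2–33% wider than those from averaged values (1/0.980 to 1/0.752).

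If averaging is kept, the minimum is to stop describing the displays as the primary-analysis data and to footnote that their SDs, quantiles and CIs understate the spread.

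The cost is a little programming on datasets that the co-primary analysis already creates.

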10.2.1.3. Schedule of Assessments for Subjects Permanently Discontinuing Randomized Treatment

Protocol Activity (Note: All visit timings are relative to Day 1)	Early Treatment Discontinuation Visit (within 2 weeks of discontinuing randomized treatment)	Day 1 through Week 52	
		Week 4, 16, 28, 40, 52 ± 2 weeks ⁷	Unscheduled
IRT system transaction	X		
SBP/DBP, HR	X (triplicate)	X	X
EKG	X		
Iron therapy, transfusions ¹	X	X	X
Urine (serum if transitioned to dialysis) pregnancy test (FRP only)	X ⁸		
HemoCue Hgb	X	X	X
Hematology ³	X	X	
Clinical chemistry ³	X	X	
Ferritin, total iron, UIBC, hepcidin, lipids, iPTH	X		
Hospitalization ¹ , transition to dialysis ¹ , kidney transplant ¹	X	X	X
Non-serious AEs, AEs of special interest, SAEs, clinical events	X	X	X
Review concomitant medications	X	X	X
Healthcare resource utilization (subject-reported)	X		
CKD-AQ. ^{5, 10}	X		
PGI-S, PGI-C ^{5, 10}	X		
SF-36 ^{5, 10}	X		
EQ-5D-5L & EQ-VAS ^{5, 6, 10}	X		
WPAI-ANS-CPV ^{4, 5, 10}	X		
ADPKD subjects only: Ultrasound	X ¹²		
ABPM sub-study (Appendix 13): 24 hour ABPM		X (Week 16)	
Record awake and sleep times		X (Week 16) ²	
24 hour urine collection (sodium, aldosterone & creatinine)		X (Week 16) ¹¹	

Schedule of Assessments for Subjects Permanently Discontinuing Randomized Treatment (Continued)

Protocol activity (visits ± 2 week) (Note: All visit timings are relative to Day 1)	Year 2 ⁷				Year 3 ⁷				Year 4 ⁷					Unscheduled	End of Study ⁹
	Week 64	Week 76	Week 88	Week 100	Week 112	Week 124	Week 136	Week 148	Week 160	Week 172	Week 184	Week 196	Week 208		
IRT system call															X
SBP/DBP, HR	X	X	X	X	X	X	X	X	X	X	X	X	X	X	X
HemoCue Hgb	X	X	X	X	X	X	X	X	X	X	X	X	X	X	
Hematology ³	X	Hgb only	X	Hgb only	X	Hgb only	X	Hgb only	X	Hgb only	X	Hgb only	X		X
Clinical chemistry ³	X		X		X		X		X		X		X		X
Hospitalization ¹ , transition to dialysis ¹ , kidney transplant ¹	X	X	X	X	X	X	X	X	X	X	X	X	X	X	X
Non-serious AEs, SAEs, AEs of special interest, clinical events	X	X	X	X	X	X	X	X	X	X	X	X	X	X	X
Review concomitant medications	X	X	X	X	X	X	X	X	X	X	X	X	X	X	X
Transition to dialysis ¹	X	X	X	X	X	X	X	X	X	X	X	X	X	X	X
ADPKD subjects only: eGFR ¹³		X		X		X		X		X		X			

1. Record in eCRF, if applicable.
2. Subject will record sleep and wake time during the ABPM session.
3. See details on hematology and clinical chemistry in Protocol Section 7.4.11.
4. If local dialect or language is available.

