10.3. Appendix 3: Assessment Windows

Data for continuous variables that are not related to time-to-event will be summarized according to the scheduled visit time period for which they were recorded in the eCRF. Unscheduled assessments will not be slotted to a particular time point, but will remain as unscheduled if they are either summarized or listed unless otherwise specified (i.e. Hgb endpoints described in Section [10.6.3](#) and BP endpoints described in Section [10.6.4](#)).

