
 For each subject, the mean of all available (on and off treatment) Hgb values during the EP (See Section 10.6.1) including any imputed and unscheduled Hgb values that were taken during this time period. Should the assessment dates for Hgb values from the Early Treatment Discontinuation visit and the End of Study visit fall within the EP, then these values will be included as unscheduled Hgb values. Hgb values from the Follow-up visit will not be included in the EP mean.
EP Hemoglobin Value for While On-Treatment Evaluable Hgb Supportive Analysis

 For each subject, the mean of all evaluable Hgb values during the EP (See Section 10.6.1) including any evaluable unscheduled Hgb values that were taken during this time period. Should the assessment dates for Hgb values from the Early Treatment Discontinuation visit and the End of Study visit fall within the EP, then these values will be included as unscheduled Hgb values. Hgb values from the Follow-up visit will not be included in the EP mean.
EP Hemoglobin Value for Alternative EP Supportive Analyses

 For each subject, the mean of all Hgb values during the Alt. EP (See Section 10.6.1) including any imputed and unscheduled Hgb values that were taken during this time period. This analysis will be conducted using all available (on and off treatment) Hgb values and separately using evaluable Hgb values only. Should the assessment dates for Hgb values from the Early Treatment Discontinuation visit and the End of Study visit fall within the Alt. EP, then these values will be included as unscheduled Hgb values. Hgb values from the Follow-up visit will not be included in the Alt. EP mean.
Use of Unscheduled Hemoglobin Values and Multiple Hgb Values on the Same Date

 The scenarios outlined below provide guidance on the use of unscheduled Hgb values and

Hemoglobin Values

- multiple Hgb values occurring on the same date. Each row represents a single calendar date.
- Rows outlining scenarios where there is at least one central lab Hgb and at least one HemoCue Hgb on the same date apply only for the derivation of Hgb values to be used in the co-primary Hgb analysis, where central lab values are used if they are available and if the central lab value is missing, then a corresponding non-missing HemoCue Hgb value is used.

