 - Rows outlining scenarios involving combinations of scheduled and unscheduled Hgb values of the same type apply to all Hgb summaries and analysis.

Scheduled Central Lab Hgb Value	Unscheduled Central Lab Hgb Value	Scheduled HemoCue Hgb Value	Unscheduled HemoCue Hgb Value	Value to Use	Type/Label
x				Scheduled central lab Hgb value	Scheduled visit
	x			Unscheduled central lab Hgb value	Unscheduled
		x		Scheduled HemoCue Hgb value	Scheduled visit
		multiple ¹		Average of scheduled HemoCue Hgb values	Scheduled visit
			x	Unscheduled HemoCue Hgb value	Unscheduled
	multiple			Average of unscheduled central lab Hgb values	Unscheduled
			multiple	Average of unscheduled HemoCue Hgb values	Unscheduled
x	x			Average of central lab Hgb values	Scheduled visit
x		x		Scheduled central lab Hgb value	Scheduled visit
x			x	Scheduled central lab Hgb value	Scheduled visit
	x	x		Unscheduled central lab Hgb value	Unscheduled
	x		x	Unscheduled central lab Hgb value	Unscheduled
		x	x	Average of HemoCue Hgb values	Scheduled visit

1: The dose adjustment algorithm will require sites to obtain two HemoCue Hgb values at some visits.

Time In Range

Time in Range During the EP

- Number of days that a subject's evaluable Hgb is within the analysis range of 10-11.5 g/dL inclusive during the EP (See Section 10.6.1), including any unscheduled evaluable Hgb values that were taken during this time period.
- Use of unscheduled Hgb values follows the scenarios for unscheduled and multiple Hgb values.
- Linear interpolation is used to estimate Hgb between visits, accounting for any intermittent missing values [Rosendaal, 1993].

Percent Time in Range During the EP

- Time in Range During the EP / [Earlier of (Date of the last evaluable Hgb value, Week 52 visit date) – Later of (Date of the first evaluable Hgb value that between Week 16 and Week 52

Time In Range

inclusive, Week 28 visit date)]
 
 Note: Percent time in/below/above range during the EP is only defined for subjects with a Treatment Stop Date that is on or after their Week 28 visit date, and have at least two evaluable Hgb values on different days, where at least one evaluable Hgb value is contained within the EP and another evaluable Hgb value occurs within the range of the Week 16 visit through 4 weeks following the Week 52 visit, inclusive.
Time in Range During the MP

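### A scheduled visit with a HemoCue result and a same-day unscheduled central Hgb is labelled unscheduled, so the co-primary analysis imputes a visit that was measured

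*SAP*

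**What the plan says.** SAP 10.6.3.1 has a table for dates with more than one Hgb value. It crosses scheduled and unscheduled values with central laboratory and HemoCue values, and gives each combination a value to use and a label. Where the column "Unscheduled Central Lab Hgb Value" and the scheduled HemoCue column are both marked, the central value is used and labelled Unscheduled. The text above the table says that rows mixing the two methods apply only to deriving values for the co-primary analysis.

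The same section defines the co-primary EP value as the mean of all available values, "including any imputed and unscheduled Hgb values that were taken during this time period". For ETD and EOS values dated in the EP it says "then these values will be included as unscheduled Hgb values".

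The imputation in 7.1.2.5 handles scheduled values. Intermittent gaps in scheduled data are filled first. Then "the missing scheduled Hgb values through Week 52 will be imputed based on the MAR assumption", and "The monotone regression will have baseline Hgb, prior scheduled (possibly imputed) Hgb values"; unscheduled values are not listed as predictors. The default in 10.3 is "Unscheduled assessments will not be slotted to a particular time point", with an exception pointing to 10.6.3 for Hgb. Section 10.6.3 contains no rule that assigns an unscheduled value to a visit by its date window.

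**The concern.** A scheduled HemoCue value on its own fills its visit. If an unscheduled central sample is taken the same day, which is the method the plan prefers, the visit loses its scheduled status. Obtaining the better measurement turns an observed visit into a missing one, and the co-primary analysis then imputes it.

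ETD and EOS values raise a milder form of the same problem. They can be the most recent Hgb before a run of missing visits, yet the missing-at-random model cannot condition on them. What is at stake is the handling of a co-primary endpoint: a time point counted twice, a measured value given less weight than it should have, and, in the tipping-point analysis, a delta shift applied to a visit that has a measured value.

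**Working it through.** **Tracing the labels (10.6.3.1).**

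| Values on the date | Value used | Label | Scheduled slot |
|---|---|---|---|
| Scheduled HemoCue only | HemoCue | Scheduled visit | filled |
| Scheduled and unscheduled HemoCue | average | Scheduled visit | filled |
| Scheduled and unscheduled central | average | Scheduled visit | filled |
| Unscheduled central, scheduled HemoCue | unscheduled central | Unscheduled | empty |

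Only in the last row does a date with a scheduled measurement end with an empty slot. Section 7.1.2.5 then imputes it. If the visit falls at the start of a monotone run, the tipping-point rule treats it as the first missed visit and shifts it by delta.

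**Which later visits are affected.** After a same-day case, none, provided they are attended. After permanent treatment discontinuation, the schedule in 10.2.1.3 keeps Weeks 28, 40 and 52 within the EP; Weeks 32, 36, 44 and 48 are not on it. After an EOS visit inside the EP, the remaining visits are missing.

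**Inputs for size.** The SAP states no figure on this point, so there is none to reproduce. From the SAP: seven scheduled EP visits (Weeks 28 to 52, every 4 weeks) and a margin of -0.75 g/dL. Assumed, because the SAP gives none: first-order autoregressive correlation rho between successive visits of 0.5, 0.7 or 0.9; a measured value d = 1.5 g/dL below its prediction; a between-arm difference of 1% to 10% in the share of affected subjects.

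**Weight of the measured value.**
- As written, it is one value beside seven scheduled or imputed ones: 1/8 = 0.125. (The small term from representing one time point twice is left out.)
- If it fills its visit and the m later visits are missing: (1 + rho + ... + rho^m)/7.

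**Same-day row, all other visits observed.** 1/7 - 1/8 = 1/56. The subject's EP mean changes by 1.5/56 = 0.027 g/dL.

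**Value followed only by missing visits** (an EOS value, or a same-day case at the last attended visit). The change is 1.5 x (slotted weight - 0.125), before rounding:

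| Visit | Slotted weight, rho 0.5 / 0.7 / 0.9 | Change in EP mean, g/dL |
|---|---|---|
| Week 32 (m = 5) | 0.281 / 0.420 / 0.669 | 0.23 / 0.44 / 0.82 |
| Week 40 (m = 3) | 0.268 / 0.362 / 0.491 | 0.21 / 0.36 / 0.55 |
| Week 52 (m = 0) | 0.143 / 0.143 / 0.143 | 0.03 / 0.03 / 0.03 |

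**Treatment difference.** At 0.36 g/dL per affected subject: 0.01 x 0.36 = 0.0036 and 0.10 x 0.36 = 0.036. The extreme corner of the table gives 0.10 x 0.82 = 0.082. For the same-day row with other visits observed: 0.01 x 0.027 = 0.0003 to 0.10 x 0.027 = 0.0027.

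**The case against.** The strongest reply is that the table applies one rule throughout: the label follows the source of the value used. The same-type rows average in a scheduled value, so they keep the scheduled label; the disputed row uses an unscheduled value, so it does not. That is right, and the table does not contradict itself. The rule is nonetheless a poor one in this row, because its only effect there is to empty a visit that a scheduled HemoCue value would have filled.

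Several stronger readings are tempting, and the SAP does not support them:
- *That measured ETD and EOS values are ignored.* Those dated in the EP enter the EP mean, so they are diluted. Only an ETD value before Week 28 is lost.
- *That all later visits are imputed as well.* Only those that are themselves missing are. Subjects are encouraged to stay in the study, and off-treatment scheduled values at Weeks 28, 40 and 52 feed the imputation.
- *That an ETD or EOS visit replaces a scheduled one.* The SAP does not say so.
- *That a same-day case counts against the per-protocol requirement of five of seven scheduled values.* Mixed-method rows are confined to the co-primary derivation, and Appendix 1 has its own HemoCue fallback.
- *That the bias has a known direction.* This would need ETD values to be typically low, which the SAP does not state.

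It is also fair that the tipping-point analysis varies monotone-missing values widely by arm, and that an observed-values-only analysis is planned. Both limit the risk to the conclusion. Neither corrects the labelling in the co-primary analysis itself.

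**Conclusion.** The point holds for the same-day row: as written, a measured visit is imputed and its time point is represented twice in the EP mean. The handling of ETD and EOS values is a secondary weakness of the same kind. The expected effect on the treatment difference is about 0.004 to 0.04 g/dL, at most about 5% of the 0.75 margin (0.036/0.75 = 0.048). Even the extreme corner of the assumed ranges reaches only 0.08. These sizes rest on assumed correlation, deviation and frequency. They carry to the treatment difference only as far as the arms differ in how often the pattern occurs. A reader might infer that the non-inferiority conclusion is at risk; nothing in the SAP supports that. The case for acting is that the rule governs a co-primary endpoint and is easily corrected before unblinding.

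**What to change.** 1. In the 10.6.3.1 table, keep the central value in the row for an unscheduled central plus a scheduled HemoCue value, but label it Scheduled visit. The visit is then not imputed and the value counts once. The cost is one table cell and the matching derivation code.
2. Preferably, add that when a scheduled Hgb through Week 52 is missing, an ETD or EOS value inside the plan's existing window for that visit is assigned to it before imputation and is not counted again as unscheduled. Use only windows the plan already has: the on-treatment windows in 10.2.1.1 (1 week either side, but 3 days for Weeks 2 and 4), and after stopping, 2 weeks either side of Weeks 4, 16, 28, 40 and 52. Weeks 32, 36, 44 and 48 have no post-discontinuation window and should not be given one by implication. Because 10.6.1 starts the EP at the Week 28 visit, also state whether a value dated before the planned Week 28 date may fill that visit.

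No new data are needed. The downside of the second change is that a few off-date values are treated as scheduled ones.
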